AIM 2: Assess the efficacy of FORT-A for decreasing the rate of opioid recidivism (using any opioid for 3 or more days in any 30-day period) compared to standard PRC care in a sample of OEF/OIF/OND polymorbid CMP Veterans discharged off of opioid medication in VA care since the start of the OSI. Unlike the original FORT trial, this research will formally and prospectively track opioid medication use among polymorbid Veterans to sensitively detect changes in chronic opioid therapy attributable to FORT-A versus PRC treatment. FORT-A is expected to produce significant reductions in the rate of opioid recidivism by imparting numerous strategies to supplant opioid medication as a pain management strategy. FORT-A will avoid the stigma of “traditional” opioid abuse treatment and provide a pain management alternative to those who have been discharged from opioid medications as part of the OSI.

EXPLORATORY AIM 3: Based on the PI’s ongoing ESCAPE trial, this research team has identified psychological processes (helplessness, perceived burdensomeness) that likely play a mechanistic role in pain management among OEF/OIF/OND deployers. We will assess these constructs twice a week and analyze latent changes in FORT-A and PRC Veterans to ascertain their role as pain management mediators

Design and Outcomes

This study is a 1:1 block randomized clinical trial comparing the FORT-A program to treatment as usual for polytrauma OEF/OIF/OND Veterans with prior persistent opioid use and chronic musculoskeletal pain who are eligible for treatment through the STVHCS Polytrauma Rehabilitation Center. All participants will be offered Physical Therapy services before enrollment and will be enrolled after completing or denying Physical Therapy (up to 12 sessions as recommended by a PRC Physical Medicine & Rehabilitation Physician ([name], [name]). If they have already completed PRC Physical Therapy before study enrollment, they will not need to do so again. Also, if the Veteran qualifies but refuses PRC Physical Therapy, he or she will still be eligible to enroll in this study and will not be asked to complete PRC PT. Veterans randomized to PRC (treatment as usual) will then meet with PRC and other VA medical providers per usual standards of care (described below). Those

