4.1 Inclusion Criteria

Study participants must meet all of the inclusion criteria below to participate in this study as follows:

- 1) Demographics for inclusion in this research include both genders, all racial/ethnic groups, and ages 18-72.
- 2) Present with chronic musculoskeletal pain (CMP) as a primary pain complaint
- 3) CMP is accompanied by at least moderate disability based on a score of 20% or more on the Oswestry Disability Index;
- 4) Consistent with NIH Task Force recommendations, "chronic" CMP has been a problem for the Veteran for at least half the days in the last 3 months and was acquired or exacerbated as part of active duty U.S. military service in the Gulf War, Operations Iraqi Freedom (OIF), Enduring Freedom (OEF), or New Dawn (OND) war eras.
- 5) CMP presents in the context of comorbid psychiatric symptoms of posttraumatic stress disorder (PTSD; based on a score of 25 or more on the PTSD Checklist-Version 5) and/or depression (based on a score of 10 or more on the PHQ-9).

6) Demonstrate prior “chronic” opioid use (defined as using opioid medication for 20 out of every 30 days over three or more months) and discharged off of persistent opioid medications on their own or by a provider for at least one week prior to the pain management program period (Weeks 1-3).

7) Speak and read/understand English well enough to fully participate in the intervention and to reliably complete assessment measures.

8) The Veteran will be eligible to be a PRC patient (i.e., have multiple trauma related physical and psychological injuries; VA, 2013) and be eligible for Physical Therapy referral through the PRC (though the referral for the same service could also come from another VHA provider). All participants will be offered Physical Therapy services before enrollment and will be enrolled after completing or denying Physical Therapy.

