6.2.2 Randomization and Baseline

Randomization (Wk -4 to 0)

Once the PI and Co-Investigators have determined that a participant has satisfactorily met all inclusion/exclusion criteria, the participant will be randomized by the study coordinator (this could be done at any time from week -4 to week 0 as long as consenting and screening come first). The date of randomization will be recorded on the Enrollment Log.

The maximum allowable time between enrollment and randomization is 4 weeks. If screening and determination of eligibility goes beyond this allowable window, the participant will need to be re-screened before randomization.

Baseline Assessments (Week 0; See Figure 4)

Baseline assessment occurs within 4 weeks from the time of enrollment (regardless of when baseline assessment occurs relative to screening, Baseline Assessment is identified as Week 0).

For participants who have successfully been screened for eligibility and are randomized into the study, baseline assessments are performed to measure the study outcomes. They also ensure that the groups are balanced with respect to baseline characteristics.

Baseline evaluations for this study include:

Assessments (Domain Assessed)	Assessment Window	Special Instructions
----------------------------------	----------------------	----------------------

Health Questionnaire / Addendum (previous pain treatments) (comorbid pain/medical conditions)	≤ 2 weeks before treatment start	Balance Sample Past medical history will not change, so this measure is only given once
Concomitant Medications and Medication Quantification Scale- III (medications that may impact pain) (medications that may impact mood)		Control: Other Medications Medications may change, so this will be assessed at all assessment visits; self-report and CPRS review
Timeline Follow-back Interview (opioid & other pain medication use)		Endpoint: Hypothesis 3 Assessed at all assessment visits
Oswestry Disability Index (self-report disability)		Endpoint: Hypothesis 1 Veterans cannot participate with moderate to severe TBI- related cognitive impairment
PHQ-9 (depression symptoms)		Endpoint: Hypothesis 2 Assessed at all assessment intervals
PTSD Checklist – 5 (PTSD symptoms)		Endpoint: Hypothesis 2 Assessed at all assessment intervals

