cohorts for FORT-A and PRC with between 3 to 7 participants (as described in Efrid, 2011). The coordinator and co-coordinator will be blinded to all randomization assignments but will initiate a treatment cohort when a sufficient number of participants have been assigned.

There is a four-week window between enrollment and baseline assessment (Week -4 to Week 0, as shown in 6.1). Study intervention must begin within 2 weeks after baseline to ensure that baseline assessment data adequately represent *current* functioning at the time of treatment, especially functional capacity evaluation [FCE] data that are used to guide the physical therapy portion of the interdisciplinary intervention. Test-retest reliability of FCE has been confirmed over a period of two weeks (Brouwer et al., 2003), with only slight fluctuations in more frequent testing resulting in a slight increase in lifting capacity if repeated across two days, likely due to practice effects (Reneman et al., 2002). Thus, intervention will generally begin within 5 weeks of enrollment.

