AIM 2: Assess the efficacy of FORT-A for decreasing the rate of opioid medication recidivism compared to standard PRC care in a sample of OEF/OIF/OND polymorbid LBP Veterans. To examine our primary hypothesis, we will compare the rate of opioid medication recidivism between the two groups monthly from baseline to 12-month follow-up. As noted above, 30-40% of TAU participants are expected to meet criteria for opioid recidivism (use of any opioid medication for 3 days or more in the last 30 days at each assessment). A statistically significant main effect will be interpreted as the groups exhibiting differential change in regards disability. Secondary analyses will be conducted using growth curve modeling (i.e., mixed effects hierarchical regression with polynomial change parameters to model differences in the trajectory of opioid use over time between the groups by time).

EXPLORATORY AIM 3: To examine the role of helplessness and perceived burdensomeness in predicting the trajectory of change over time, we will use latent

growth curve modeling. We will first model the trajectory of change in the two primary outcomes as a function of group (Aim 1 and Aim 2). We will then model the trajectories of helplessness and perceived burdensomeness as a function of group. Assuming both associations are observed (i.e., that group status is related to changes in the outcomes and the mediators), we will conduct hierarchical entry of group status and each mediator to examine if group status is still associated with outcome after adjusting for changes in the mediators. This will allow us to assess the role of the mediators in predicting the outcome and the proportion of change trajectory attributed to changes in these mediators.

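### Section 9.6 gives no start date for Aim 2 recidivism, so opioid use that eligibility permits before the program can be scored as recidivism at the baseline interview

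*Combined protocol and SAP*

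**What the plan says.** **Scoring rule.** Section 9.6, Aim 2: "we will compare the rate of opioid medication recidivism between the two groups monthly from baseline to 12-month follow-up". An assessment is positive on "use of any opioid medication for 3 days or more in the last 30 days at each assessment". The Precis defines recidivism as "using any opioid for 3 or more days in any 30-day period", and Section 3 is similar. None of these gives a first countable day.

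**Measure.** Section 9.5.2 makes the TLFB the primary opioid measure, a day-by-day calendar covering 30 days. Sections 5.4, 6.1 and 6.2.4 schedule it at baseline, post-treatment, six and 12 months, and monthly by telephone; 6.1 also marks it at screening.

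**Eligibility.** Criterion 6 in Section 4.1 requires prior chronic use and being off opioids "for at least one week prior to the pain management program period (Weeks 1-3").

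**Timing.** Section 6.2.2 on randomization: "this could be done at any time from week -4 to week 0 as long as consenting and screening come first". On baseline: "Baseline assessment occurs within 4 weeks from the time of enrollment", and it is done for participants who "are randomized into the study, baseline assessments are performed to measure the study outcomes". On treatment: "Study intervention must begin within 2 weeks after baseline".

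**Time point.** Hypothesis 3 (Section 1.1) and Section 9.1 put the comparison at 12 months. Sections 9.2 and 9.6 describe monthly comparison over the year.

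**Screening.** The TLFB row in Section 6.2.1 asks for opioid use on 20 of 30 days over the past three months. Section 4 requires a prior user taken off opioids by a VA provider. Criterion 6 allows stopping on one's own or through a provider.

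**The concern.** Recidivism means return to use after stopping. A 30-day look-back at baseline reaches well behind the single opioid-free week, so a participant who followed the eligibility rule exactly can be positive before any treatment. Two analysts following Section 9.6 could score different occasions and report different rates.

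Use before randomization is expected to be similar in the two arms, so the likely effect of scoring it is dilution. Baseline follows randomization, however, so some of its look-back days may fall after assignment, and balance is not guaranteed for those days. The whole baseline calendar is therefore neither a sound outcome nor a clean pre-randomization covariate.

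The plan also leaves open which Aim 2 comparison, 12-month or monthly, is the main one.

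**Working it through.** **1. The plan's own figure.** Section 9.2: 45% versus 22.5%, 65 per arm, alpha 0.05 (two-sided assumed), power 0.80.

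- Standard error under the alternative: sqrt[(0.45×0.55 + 0.225×0.775)/65] = 0.0806.
- Standard error under the null, pooled rate 0.3375: sqrt[2×0.3375×0.6625/65] = 0.0829.
- Pooled: (0.225 − 1.96×0.0829)/0.0806 = 0.775, power 0.78.
- Unpooled: 0.225/0.0806 − 1.96 = 0.833, power 0.80.

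The stated power reproduces and does not depend on the baseline occasion.

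**2. Day count.** Day 0 is the first program day. The minimum opioid-free week is days −7 to −1, so permitted use is day −8 or earlier. An interview on day v covers days v−30 to v−1. For v from −7 to 22, permitted days = 23 − v, not below 0; for earlier visits the count is 30.

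| Baseline interview | Permitted-use days of 30 |
|---|---|
| Day 0 | 23 |
| Day −3 (example log in Section 5.4) | 26 |
| Day −7 to −14 | 30 |

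Counting the interview day itself lowers the figures for days −7 to 0 by one. The 3-day threshold can be met by permitted use alone at every allowed baseline date.

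**3. Post-treatment visit.** Assume a Monday start with sessions on Monday, Tuesday, Thursday and Friday, so the last session is day 18. Permitted days are 5, 4, 3 and 2 for visits on days 18, 19, 20 and 21 (one fewer each if the interview day counts). Only a visit within about 2 days of the last session can reach 3, and only for someone who stopped at the minimum. Section 5.4 does advise scheduling with the last treatment day. At Week 4 (day 21) or later, and in the example log (day 21), it cannot happen.

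**4. Monthly calls.** The earliest call is one 28-day month after a day-18 visit, less the one-week tolerance: 18 + 28 − 7 = day 39. Its window starts on day 9, so it holds no pre-program days.

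**5. Days after randomization: extremes of the stated windows.** Randomization may precede baseline by 0 to 28 days, so 0 to 28 baseline look-back days can fall after it. The longest gap from randomization to program start is 28 + 14 = 42 days, with use permitted on up to 42 − 7 = 35. Section 6.2.2 expects treatment to start generally within about five weeks of consent, so these are corner cases.

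**6. Dilution, illustration only.** Suppose the analysis used an ever-positive rate that included baseline. Let a share q in each arm be positive at baseline through permitted use alone, independently of later use. The documents give no q. Each rate p becomes q + (1−q)p.

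| q (assumed) | Rates | Power (pooled) |
|---|---|---|
| 0 | 45% vs 22.5% | 0.78 |
| 0.1 | 50.5% vs 30.2% | 0.66 |
| 0.2 | 56% vs 38% | 0.54 |
| 0.3 | 61.5% vs 45.8% | 0.44 |
| 0.5 | 72.5% vs 61.3% | 0.27 |

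A month-by-month analysis would be affected less, because only one occasion is contaminated.

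**The case against.** The best defence is that return to use is naturally scored after baseline, and that the phrase about starting from baseline only marks the beginning of follow-up. Sections 1.1 and 9.1 name 12 months, and 9.2 speaks of monthly follow-ups. This is plausible and may be what was meant. It narrows the problem to one occasion, if that occasion is scored. It does not remove it, because the operative sentence in 9.6 runs from baseline and applies the rule at every assessment.

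Four stronger readings are tempting and are not supported:

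- **That the plan positively requires baseline to be scored**, because the baseline table in 6.2.2 labels the TLFB a Hypothesis 3 endpoint. The same table labels the baseline Oswestry score a Hypothesis 1 endpoint, and 9.6 uses that score as a covariate. The label identifies the measure, not the scored occasions.
- **That counting occasions settles the matter.** The TLFB is given at calls and at visits, and the documents do not say which of these make up the 12 periods in 9.2.
- **That the arms are biased in a known direction.** Section 9.2 says participants cannot be masked, but nothing says they learn their arm before baseline. Some baseline look-back days can follow randomization; whether behaviour on them differs by arm is unknown.
- **That the screening row and criterion 6 can never both be met.** Someone using on 20 of 30 days at screening could stop in time. The clear conflict concerns veterans who have been off opioids for longer.

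**Conclusion.** The point stands as a should-fix on a secondary aim. As written, the Aim 2 rule can classify permitted pre-program use as recidivism at baseline, with 23 to 30 of 30 look-back days exposed and 3 sufficient. The day counts rest on the minimum one-week abstinence and the stated visit windows. The share of participants affected and the resulting dilution are unknown; the power table above is illustrative.

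The 12-month comparison, read as the 30-day look-back at that visit, is untouched, as are the monthly calls and the 9.2 power basis. Post-treatment leakage is marginal.

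Two related inconsistencies are real: 12-month versus monthly as the main comparison, and the current-use screening threshold against the prior-use rules. Section 4 and criterion 6 also differ from each other on who stopped the opioid.

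**What to change.** 1. In 9.5.2 and 9.6, state that recidivism is scored only at assessments after baseline. State also that look-back days before the start of the 3-week treatment period do not count. Assign that start a calendar date the same way in both arms; usual care needs this spelled out, and the cohorts that 6.2.2 plans for both arms offer a basis. List opioid days between randomization and that date by arm.
   - *Downside:* those days are not scored, and an early post-treatment visit has a shorter window (18 countable days for a visit on day 18).
   - *Limit:* the listing is complete only where calendars cover the gap. With baseline on day −14 and a post-treatment visit on day 18, 21, 25 or 32, the number of pre-program days in no calendar is 2, 5, 9 or 14.
2. Use pre-randomization TLFB use as a covariate, not an outcome: either the screening TLFB or the baseline calendar cut at randomization. If the screening row applies as written, everyone has at least 20 of 30 days and the screening value will vary little, so settle item 4 first.
3. Name either the 12-month comparison (1.1, 9.1) or the monthly comparison (9.2, 9.6) as the main Aim 2 analysis and label the other secondary.
4. Separately, reconcile the TLFB row in 6.2.1 with Section 4 and criterion 6, and those two with each other. Which rule applies is the sponsor's decision.

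The cost is wording in 9.5.2 and 9.6 plus reconciled eligibility text. The TLFB is already a daily calendar at the visits needed, so no new instrument is required.

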10. DATA COLLECTION AND QUALITY ASSURANCE

10.1 Data Collection Forms

Data will be collected by an Independent Evaluator blind to the randomized condition of the participant and entered into an online SQL database on the STRONG STAR server that is designed specifically for this study. As described in the STRONG STAR Data Entry SOP (see **Appendix S**), data are double-entered to minimize transcription errors and all data entry forms include appropriate data entry masks that limit the format and scope of entered data (to ensure that out-of-range values are not erroneously recorded) with provided feedback if entered data exceed expected ranges. STRONG STAR has developed strict rules guiding the translation of assessment measures and data recording forms into digital formats as outlined in **Appendix T**. Paper copies of assessments are also uploaded and tagged to the assessment record for review by the IEs or other study staff if adjudication of responses is needed. The STRONG STAR Network is FISMA compliant and has received permission from the VHA for the storage of Veteran study data (which is very strictly controlled by the VA system). Because the STRONG STAR Database is accessible through a secure internet portal, data can be entered into the system directly from any VA computer with internet access (of which this study currently has dedicated access to two through the PRC). To ensure confidentiality of patient records, all data are entered into study records using the participant's unique ID. A link between identifiers and the ID is maintained in a separate data table with access restricted to individuals who are not blind to patient identifiers (e.g., study Coordinator, interventionists).

10.2 Data Management

Data will be coded using an assigned number. Data collected during treatment will be entered into a secure STRONG STAR database, and hardcopies will be placed into a lock box which will be transported by car to University of Texas Health Science Center San Antonio (UTHSCSA) STRONG STAR offices by a STRONG STAR staff member who will place it into the locked cabinets at the STRONG STAR offices. Audio and video recordings will be uploaded to a secure STRONG STAR server over an encrypted network connection between VA networks and UTHSCSA networks. Members of the study team will have access to the data. Every member of the Research Team will be trained and monitored about how to handle and protect both medical and research records. Furthermore, the Research Team strictly controls access to study data using policies and procedures developed specifically for the

STRONG STAR Research Consortium. Adverse Events will be immediately brought to the study PI and reported to the IRB and funding agency. AE's will be identified by unique identifier to protect blinding of the PI. If the participant's identity is needed to effectively manage an AE, then the Study Coordinator will link the unique identifier to the specific participant (the Coordinator will maintain a link between PHI and unique identifiers through the STRONG STAR Data Core dashboard). A STRONG STAR Data Safety and Monitoring Plan (DSMP) has been developed in accordance with the National Institutes of Health (NIH) Office of Human Research Protection (OHRP) to assure the appropriate clinical safety monitoring of study subjects participating in all of its studies. The STRONG STAR database has been certified as FISMA-compliant and has been formally cleared for the management of Veteran data through the VA.

10.3 Quality Assurance

10.3.1 Training

Sections 5.1, 5.2, and 5.4 of this protocol describe various components of training for assessment and intervention for this study. STRONG STAR uses circumscribed certification processes for assessment and intervention to ensure that individuals completing assessment and intervention are trained to an acceptable standard and that resulting assessment and intervention is of sufficient quality to provide and sensitively assess systematic treatment effect to the greatest extent possible.

10.3.2 Quality Control Committee

A STRONG STAR Research Assistant outside of this study will be asked to complete a quarterly External Protocol Monitoring Checklist (**Appendix U**) for submission to the Study Coordinator, PI, and the STRONG STAR Admin Core for review. Discrepancies or problems will be addressed by the Admin Core and the PI acting as the quality control committee.

10.3.3 Metrics

As shown in **Appendix U**, quality control metrics include appropriate organization of study documents, confirmation of regulatory document versions, verification of enrollment protocols, documentation and adjudication of AEs, storage of data, and documentation/report/adjudication of protocol deviations.

10.3.4 Protocol Deviations

The STRONG STAR Protocol Deviation and AE SOP (**Appendix V and W**) thoroughly describes the mechanisms and responsibilities for tracking, documenting, and adjudicating protocol deviations. Briefly, each participant chart will include a Protocol Variance and Deviation Log that will be used to track and document deviations from protocol. Responsibility for tracking deviations lies with the study staff member who first discovers a provider or participant deviation from protocol (advertent or inadvertent). STRONG STAR Regulatory (aka the STRONG STAR Admin Core) is responsible for working with the PI and the Coordinator to assess the nature of the deviation and the adjudication of the deviation. Deviations are entered

in the STRONG STAR Database, reported to the IRB (the SOP describes the BAMC IRB, but this protocol will report to the UTHSCSA and VA IRBs), and included in annual reports to the funder.

